8.3.2 DEFINITION OF SERIOUS ADVERSE EVENTS (SAE)

Serious adverse event or serious suspected adverse reaction. An AE or suspected adverse reaction is considered "serious" if, in the view of either the investigator or sponsor, it results in any of the following outcomes: death, a life-threatening adverse event, inpatient hospitalization or prolongation of existing hospitalization, a persistent or significant incapacity or substantial disruption of the ability to conduct normal life functions, or a congenital anomaly/ birth defect. Important medical events that may not result in death, be life-threatening, or require hospitalization

may be considered serious when, based upon appropriate medical judgment, they may jeopardize the patient or subject and may require medical or surgical intervention to prevent one of the outcomes listed in this definition. Examples of such medical events include allergic bronchospasm requiring intensive treatment in an emergency room or at home, blood dyscrasias or convulsions that do not result in inpatient hospitalization, or the development of drug dependency or drug abuse.

Note: In addition to the above criteria, adverse events meeting either of the below criteria, although not serious per ICH definition, are reportable to the Merck in the same timeframe as SAEs to meet certain local requirements. Therefore, these events are considered serious by Merck for collection purposes.

- Is a new cancer (that is not a condition of the study);
- Is associated with an overdose.

All AEs, meeting serious criteria from the time of study treatment through 90 days following cessation of study treatment, or 30 days following cessation of study treatment if the participant initiates new anticancer therapy, whichever is earlier must be collected by the delegated study staff.

Refer to Table in Section 8.4.3.1 for additional details regarding each of the above criteria.

8.3.3 CLASSIFICATION OF AN ADVERSE EVENT

8.3.3.1 SEVERITY OF EVENT

For AEs not included in the protocol-defined grading system, the following guidelines will be used to describe severity.

The adverse event severity grading scale for the NCI CTCAE (v5.0) will be used for assessing adverse event severity. The following table will be used for assessing severity for adverse events that are not specifically listed in the NCI CTCAE (v5.0).

V5.0 CTCAE Grading	
Grade 1	Mild; asymptomatic or mild symptoms; clinical or diagnostic observations only; intervention not indicated.
Grade 2	Moderate; minimal, local or noninvasive intervention indicated; limiting age-appropriate instrumental ADL.
Grade 3	Severe or medically significant but not immediately life-threatening; hospitalization or prolongation of hospitalization indicated; disabling; limiting self-care ADL.
Grade 4	Life threatening consequences; urgent intervention indicated.
Grade 5	Death related to AE

NCI CTCAE □ National Cancer Institute Common Terminology Criteria for Adverse Events. Note: Based on the most recent version of NCI CTCAE (v5.0), which can be found at:

http://ctep.cancer.gov/protocolDevelopment/electronic_applications/ctc.htm

Instrumental activities of daily living refer to preparing meals, shopping for groceries or clothes, using the telephone, managing money, etc.

Examples of self-care activities of daily living include bathing, dressing and undressing, feeding oneself, using the toilet, and taking medications, as performed by patients who are not bedridden.

If an event is assessed as a "significant medical event," it must be reported as a serious adverse event.

8.3.3.2 RELATIONSHIP TO STUDY INTERVENTION

The clinician's assessment of an AE's relationship to study agent (drug, biologic, device) is part of the documentation process, but it is not a factor in determining what is or is not reported in the study. If there is any doubt as to whether a clinical observation is an AE, the event should be reported. All AEs must have their relationship to the study agent assessed. In a clinical trial, the study product must always be suspect. To help assess, the following guidelines are used.

For all collected AEs, the clinician who examines and evaluates the participant will determine the AE's causality based on temporal relationship and his/her clinical judgment. The degree of certainty about causality will be graded using the categories below.

- **Definitely Related** – There is clear evidence to suggest a causal relationship, and other possible contributing factors can be ruled out. The clinical event, including an abnormal laboratory test result, occurs in a plausible time relationship to drug administration and cannot be explained by concurrent disease or other drugs or chemicals. The response to withdrawal of the drug (dechallenge) should be clinically plausible. The event must be pharmacologically or phenomenologically definitive, with use of a satisfactory rechallenge procedure if necessary.
- **Probably Related** – There is evidence to suggest a causal relationship, and the influence of other factors is unlikely. The clinical event, including an abnormal laboratory test result, occurs within a reasonable time after administration of the drug, is unlikely to be attributed to concurrent disease or other drugs or chemicals, and follows a clinically reasonable response on withdrawal (dechallenge). Rechallenge information is not required to fulfill this definition.
- **Possibly Related** – There is some evidence to suggest a causal relationship (e.g., the event occurred within a reasonable time after administration of the trial medication). However, other factors may have contributed to the event (e.g., the participant's clinical condition, other concomitant events). Although an AE may rate only as "possibly related" soon after discovery, it can be flagged as requiring more information and later be upgraded to "probably related" or "definitely related", as appropriate.
- **Unlikely to be Related** – A clinical event, including an abnormal laboratory test result, whose temporal relationship to drug administration makes a causal relationship improbable (e.g., the event did not occur within a reasonable time after administration

of the trial medication) and in which other drugs or chemicals or underlying disease provides plausible explanations (e.g., the participant's clinical condition, other concomitant treatments).

- **Not Related** – The AE is completely independent of study drug administration, and/ or evidence exists that the event is definitely related to another etiology. There must be an alternative, definitive etiology documented by the clinician.

8.3.3.3 EXPECTEDNESS

Expectedness will only be documented for SAEs. Study Principal Investigator with collaboration with the Sponsor will be responsible for determining whether an SAE is expected or unexpected. An SAE will be considered unexpected if the nature, severity, or frequency of the event is not consistent with the risk information previously described for the study agent.

8.3.4 TIME PERIOD AND FREQUENCY FOR EVENT ASSESSMENT AND FOLLOW-UP

The occurrence of an AE or SAE may come to the attention of study personnel during study visits and interviews of a study participant presenting for medical care, or upon review by a study monitor. All AEs including local and systemic reactions not meeting the criteria for SAEs will be captured on the appropriate CRF. Information to be collected includes event description, time of onset, clinician's assessment of severity, relationship to study product (assessed only by those with the training and authority to make a diagnosis), and time of resolution/ stabilization of the event. All AEs occurring while on study must be documented appropriately regardless of relationship. All AEs will be followed to adequate resolution.

Any medical condition that is present at the time that the participant is screened will be considered as baseline and not reported as an AE. However, if the study participant's condition deteriorates at any time during the study, it will be recorded as an AE. UAPs will be recorded in the data collection system throughout the study.

Changes in the severity of an AE will be documented to allow an assessment of the duration of the event at each level of severity to be performed. AEs characterized as intermittent require documentation of onset and duration of each episode.

The PI will record all reportable events during the designated protocol specified timelines according to Section 8.4.1. SAEs will be followed until resolution or stabilization. At each study visit, the investigator will inquire about the occurrence of AE/SAEs since the last visit.

8.3.5 ADVERSE EVENT REPORTING

The investigator must record non-serious adverse events and report to DSMC and IRB according to timetable for reporting specified in section 10.1.5.

8.3.5.1 DEFINITION OF AN OVERDOSE FOR THIS PROTOCOL AND REPORTING OF OVERDOSE TO THE SPONSOR-INVESTIGATOR AND TO MERCK

For purposes of this study, an overdose of pembrolizumab will be defined as any dose of 1,000 mg or greater (≥ 5 times the indicated dose). No specific information is available on the treatment of overdose of pembrolizumab. In the event of overdose, the participant should be observed closely for signs of toxicity. Appropriate supportive treatment should be provided if clinically indicated.

If an adverse event(s) is associated with (“results from”) the overdose of a Merck product, the adverse event(s) is reported as a serious adverse event, even if no other seriousness criteria are met.

If a dose of Merck’s product meeting the protocol definition of overdose is taken without any associated clinical symptoms or abnormal laboratory results, the overdose is reported as a non-serious Event of Clinical Interest (ECI), using the terminology “accidental or intentional overdose without adverse effect.”

All reports of overdose with and without an adverse event must be reported within 24 hours via SAE form to the Sponsor-Investigator and within 2 working days to Merck Global Safety. (Attn: Worldwide Product Safety; [contact])

8.3.6 SERIOUS ADVERSE EVENT REPORTING

The Sponsor-Investigator must notify FDA and all participating PIs in an IND safety report of potential serious risks as soon as possible, but in no case later than 15 calendar days after the Sponsor-Investigator determines that the information qualifies for reporting. (21 CFR 312.32(c)(1))

The Sponsor-Investigator must notify FDA of any unexpected fatal or life-threatening adverse reactions as soon as possible, but in no case later than 7 calendar days after the Sponsor-Investigator’s initial receipt of the information. (21 CFR 312.32(c)(2)).

All SAEs will be followed until satisfactory resolution or until the site PI deems the event to be chronic or the adherence to be stable. Other supporting documentation of the event may be requested by the sponsor-investigator and should be provided as soon as possible.

The Sponsor-Investigator will be responsible for notifying FDA of any unexpected fatal or life-threatening suspected adverse reaction as soon as possible but in no case later than 7 calendar days after the Sponsor-Investigator's initial receipt of the information.

All SAEs will be reported using the FDA 3500A Mandatory MedWatch report form. SAE form can be found at:

<http://www.fda.gov/downloads/AboutFDA/ReportsManualsForms/Forms/UCM048334.pdf>

To submit an SAE, email as follows within 24 hours of becoming aware of the event:

To: [contact]

[contact]

Subject: 21-4129 SAE Report Form

Attach: SAE form completed and signed by the Investigator

Body of Email: List the following information as assessed by the Investigator

- Whether the event is expected or unexpected
- Causality of events in relation to all study medications
- Whether the SAE is related to disease progression
- CTCAE grade

Reporting of AEs, SAEs, and Other Reportable Safety Events to Merck

Individual AE reports including SAEs and other relevant safety information are to be reported via Merck Safety Reporting Portal available at this link: <https://safetyreporting.merck.com>.

In the event the Safety Portal is experiencing technical difficulties, and the AE information cannot be uploaded, or the acknowledgement was not received, the AE information should be faxed to the Merck GPV [contact], or toll-free [contact]. If fax confirmation is not received within one (1) business day, Principal Investigator/Institution will contact Merck to determine if the original report needs to be re-sent. It should be noted that the Safety Portal should only be used for individual adverse event reporting. Principal Investigator/Institution will maintain a record of the confirmation.

The investigator must record all serious adverse events and report to DSMC and IRB according to timetable for reporting specified in section 10.1.5. Per institutional policy, all serious adverse

events occurring at UCCC/UCHealth will be entered into OnCore according to timetable for reporting specified in section 10.1.5.

The study clinician will complete an SAE Form within the following timelines:

- All deaths and immediately life-threatening events, whether related or unrelated, will be recorded on the SAE Form and submitted to the Merck within 2 working days.
- Other SAEs, regardless of relationship, will be submitted to the Sponsor-Investigator within 24 hours of site awareness and within 2 days to Merck via fax number listed.

For the time period beginning when the consent form is signed until treatment allocation/randomization, any serious adverse event, or follow up to a serious adverse event, including death due to any cause that occurs to any participant must be reported within 24 hours to the Sponsor-Investigator and within 2 working days to Merck Global Safety if it causes the participant to be excluded from the trial, or is the result of a protocol-specified intervention, including but not limited to washout or discontinuation of usual therapy, diet, placebo treatment or a procedure.

For the time period beginning at treatment allocation/randomization through 90 days following cessation of treatment, or 30 days following cessation of treatment if the participant initiates new anticancer therapy, whichever is earlier, any serious adverse event, or follow up to a serious adverse event, including death due to any cause whether or not related to the Merck product, must be reported within 24 hours to the Sponsor-Investigator and within 2 working days to Merck Global Safety.

Additionally, any serious adverse event, considered by an investigator who is a qualified physician to be related to Merck product that is brought to the attention of the investigator at any time following consent through the end of the specified safety follow-up period specified in the paragraph above, or at any time outside of the time period specified in the previous paragraph also must be reported immediately to Merck Global Safety.

All participants with serious adverse events must be followed up for outcome.

A copy of all 15 Day Reports and Annual Progress Reports is submitted as required by FDA, European Union (EU), Pharmaceutical and Medical Devices agency (PMDA) or other local regulators. Investigators will cross reference this submission according to local regulations to the Merck Investigational Compound Number (IND, CSA, etc.) at the time of submission. Additionally investigators will submit a copy of these reports to Merck & Co., Inc. (Attn: Worldwide Product Safety; [contact]) at the time of submission to FDA.

Follow-up of unresolved serious adverse events

Any SAEs that are unresolved at the time of the initial report submission should be followed up by the investigator for as long as medically indicated, and an updated SAE report submitted at the

time new information regarding the event becomes available.

8.3.6.1 ADVERSE EVENT OF SPECIAL INTEREST (AESI)

Selected non-serious and serious adverse events are also known as Adverse Events of Significant Interest (AESI) and must be reported via FDA 3500A Mandatory MedWatch form within 2 working days to Merck Global Safety. (Attn: Worldwide Product Safety; [contact]).

For the time period beginning when the consent form is signed until treatment allocation/randomization, any AESI, or follow up to an AESI, that occurs to any participant must be reported within 2 working days to Merck Global Safety if it causes the participant to be excluded from the trial, or is the result of a protocol-specified intervention, including but not limited to washout or discontinuation of usual therapy, diet, placebo treatment or a procedure.

For the time period beginning at treatment allocation/randomization through 90 days following cessation of treatment, or 30 days following cessation of treatment if the participant initiates new anticancer therapy, whichever is earlier, any AESI, or follow up to an AESI, whether or not related to Merck product, must be reported within 2 working days to Merck Global Safety.

Adverse events of special interest for this trial include:

1. An overdose of Merck product, as defined in Section 8.4.5.1 - Definition of an Overdose for This Protocol and Reporting of Overdose to the Sponsor-Investigator, that is not associated with clinical symptoms or abnormal laboratory results.
2. All Potential DILI events meeting biochemical criteria of Hy's law will be reported regardless of suspected etiology to the Sponsor as a SAE, within 2 business days but no longer than 3 calendar days, with other medical event (OME) criteria in the absence of other SAE criteria. Potential DILI/DILI events are defined as:

an elevated AST or ALT lab value that is greater than or equal to 3X the upper limit of normal and an elevated total bilirubin lab value that is greater than or equal to 2X the upper limit of normal and, at the same time, an alkaline phosphatase lab value that is less than 2X the upper limit of normal, as determined by way of protocol-specified laboratory testing or unscheduled laboratory testing.*

*Note: These criteria are based upon available regulatory guidance documents. The purpose of the criteria is to specify a threshold of abnormal hepatic tests that may require an additional evaluation for an underlying etiology.

8.3.7 REPORTING OF PREGNANCY AND LACTATION TO THE SPONSOR- INVESTIGATOR AND TO MERCK

Pregnancies and infant exposures during breastfeeding that occur after the consent form is

signed but before treatment allocation/randomization must be reported by the investigator if they cause the participant to be excluded from the trial, or are the result of a protocol-specified intervention, including but not limited to washout or discontinuation of usual therapy, diet, placebo treatment or a procedure.

Pregnancies and infant exposures during breastfeeding that occur from the time of treatment allocation/randomization through 120 days following cessation of investigational therapy, or 30 days following cessation of treatment if the participant initiates new anticancer therapy, whichever is earlier, must be reported by the investigator as an Adverse Event. All reported pregnancies must be followed to the completion/termination of the pregnancy. Pregnancy outcomes of spontaneous abortion, missed abortion, benign hydatidiform mole, blighted ovum, fetal death, intrauterine death, miscarriage and stillbirth must be reported as SAEs (Important Medical Events). If the pregnancy continues to term, the outcome (health of infant) must also be reported.

Such events must be reported within 24 hours to the Sponsor-Investigator and within 2 working days to Merck Global Safety. (Attn: Worldwide Product Safety; [contact])

8.4 UNANTICIPATED PROBLEMS

8.4.1 DEFINITION OF UNANTICIPATED PROBLEMS (UAP)

The Office of Human Research Protection (OHRP) considers unanticipated problems involving risks to participants or others to include, in general, any incident, experience, or outcome that meets **all** of the following criteria:

- Unexpected in terms of nature, severity, or frequency given (a) the research procedures that are described in the protocol-related documents, such as the IRB-approved research protocol and informed consent document; and (b) the characteristics of the participant population being studied;
- Related or possibly related to participation in the research (“possibly related” means there is a reasonable possibility that the incident, experience, or outcome may have been caused by the procedures involved in the research); and
- Suggests that the research places participants or others at a greater risk of harm (including physical, psychological, economic, or social harm) than was previously known or recognized.

This study will use the OHRP definition of UAP.

8.4.2 REPORTING OF UNANTICIPATED PROBLEMS

Incidents or events that meet the OHRP criteria for UAPs require the creation and completion of a UAP report. It is the Site PI’s responsibility to report UAPs to their IRB. The Lead PI is

responsible for reporting the UAP to the IRB and the UCCC DSMC. The UAP report will include the following information:

- Protocol-identifying information: protocol title and number, PI's name, and the IRB project number;
- A detailed description of the event, incident, experience, or outcome;
- An explanation of the basis for determining that the event, incident, experience, or outcome represents a UAP;
- A description of any changes to the protocol or other corrective actions that have been taken or are proposed in response to the UAP.

9 STATISTICAL CONSIDERATIONS

9.1 STATISTICAL HYPOTHESES

Primary Endpoint:

- Objective Response Rate (ORR per RECIST 1.1) of unirradiated tumors

Secondary Endpoints:

- Overall Survival (OS) from the initiation of therapy to the date of death or to the date of last follow-up.
- Progression Free Survival (PFS) from the initiation of therapy to the date of progression or to the date of last follow-up.
- Duration of response (DoR) defined as the time from documentation of tumor response to disease progression.
- Disease control rate (DCR) defined as the sum of partial (PR), complete response (CR) and SD.
- Treatment-emergent adverse events (AEs), serious adverse events (SAEs)

Exploratory Endpoints:

- Immune changes in tumor tissue and plasma at baseline compared to after combination SBRT/olaparaib and after Olaparib/pembrolizumab
- Assess response based on HRD status, PD-L1 expression, MMR/MSI, and TMB in tumor
- Changes in cytokines, ctDNA in plasma/serum
- Abscopal effect based on irradiated disease site

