3 OBJECTIVES AND ENDPOINTS

OBJECTIVES	ENDPOINTS	JUSTIFICATION FOR ENDPOINTS
Primary		
To assess the anti-tumor efficacy of combined therapy as determined by measurement of objective response rate (ORR)	Objective Response Rate (ORR per RECIST 1.1) of unirradiated tumors	Objective Response Rate is an established clinical endpoint for gastric and gastroesophageal junction adenocarcinomas. ORR of unirradiated tumors is to evaluate for an abscopal effect.
Secondary		
To assess the anti-tumor efficacy of combined therapy	Overall Survival (OS) from the initiation of therapy to the	Although the study is not designed or powered to

as determined by measurement of overall survival (OS), progression free survival (PFS), duration of response (DOR) and disease control rate (DCR) as a total cohort and HRD versus HR proficient.
 
To evaluate the safety and tolerability of radiotherapy added to Olaparib.
	
date of death or to the date of last follow-up.
 
Progression Free Survival (PFS) from the initiation of therapy to the date of progression or to the date of last follow-up.
 
Duration of response (DoR) defined as the time from documentation of tumor response to disease progression.
 
Disease control rate (DCR) defined as the sum of partial (PR), complete response (CR) and SD.
 
Treatment-emergent adverse events (AEs), serious adverse events (SAEs),
	
compare overall survival and progression free survival with other regimens, OS and PFS will provide preliminary data regarding efficacy of the regimen. DOR and DCR will also provide preliminary efficacy data.
 
Toxicity will be assessed according to NCI CTCAE v5.0

Tertiary/Exploratory		

To define the effect of HRD on combination SBRT, olaparib, and pembrolizumab on immunomodulation as measured by immune cell infiltration and activation in plasma/serum assays and tissue.
	
Immune changes in tumor tissue and plasma at baseline compared to after combination SBRT/olaparaib and after olaparib/pembrolizumab
 
Assess response based on HRD status, PD-L1 expression, MMR/MSI, and TMB in tumor
 
Changes in cytokines, ctDNA in plasma/serum
 
Abscopal effect based on irradiated disease site
	
This endpoint will demonstrate exploratory data to evaluate key immune and DNA Damage Response and Repair pathway biomarkers that may predict for treatment response.

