Patients will undergo serial tumor biopsies as depicted in the Trial Diagram below. Restaging will occur every 9 weeks. If at first restaging there is no evidence of progressive disease (PD), as determined by RECIST v1.1 and immune-related RECIST (irRECIST) criteria, and the patient is tolerating therapy, then patient will continue with study therapy, with clinic visits and lab work on Day 1 of future cycles and restaging imaging every 9 weeks. Patients will continue to remain on study as long as there is no evidence of PD (according to RECIST v1.1 and irRECIST criteria) and the therapy is adequately tolerated. For patients who demonstrate a response beyond 2 years of trial therapy, they will continue with olaparib treatment alone.

Serial tumor biopsies and blood samples will be taken to assess immune changes in tumor tissue and plasma at baseline compared to after combination SBRT/olaparib and after olaparib/pembrolizumab, assess response based on HRD status, PD-L1 expression, MMR/MSI, and TMB in tumor, changes in cytokines, ctDNA in plasma/serum

Patients will undergo the treatment and biopsy schedule as detailed above. However, in the event that tumor is inaccessible, the biopsy is not in the subject's best interest, or the patient refuses biopsy during course of the study, this will be documented and patients will be allowed to remain on study. Additionally, patients will continue to remain on study as long as there is no evidence of PD (according to RECIST v1.1 criteria and irRECIST) and the therapy is adequately tolerated. Interim analyses to assess secondary endpoints of OS and PFS will be scheduled to occur at 12 months and 24 months. For patients who demonstrate a response beyond 2 years of trial therapy, they will continue with olaparib treatment alone.

We plan to enroll 26 patients (13 HR deficient, 13 HR proficient).

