8.1.4.3 POST-TREATMENT VISITS

Safety Follow-Up Visit

The mandatory Safety Follow-Up Visit should be conducted approximately 30 days after the last dose of study treatment or before the initiation of a new anti-cancer treatment, whichever comes first. If the post-trial visit occurs less than 30 days after the last dose of study treatment, a subsequent follow-up phone call should be made at 30 days post the last dose of study treatment to determine if any adverse events have occurred since the post-trial clinic visit. All AEs that occur prior to the Safety Follow-Up Visit should be recorded. Participants with an AE of Grade > 1 will be followed until the resolution of the AE to Grade 0-1 or until the beginning of a new anti-cancer therapy, whichever occurs first. SAEs that occur within 90 days of the end of treatment or before initiation of a new anti-cancer treatment will also be followed and recorded. Participants who are eligible for retreatment/crossover with pembrolizumab (as described in Appendix 7) may have up to two safety follow-up visits, one after the Initial Treatment Period and one after the Second Course Treatment.

Follow-Up Visits

Participants who discontinue study treatment for a reason other than disease progression will move into the Follow-Up Phase and should be assessed every 12 weeks (42 ± 7 days) by radiologic imaging to monitor disease status. Every effort should be made to collect information regarding disease status until the start of new anti-cancer therapy, disease progression, death, end of the study or if the participant begins retreatment with pembrolizumab as detailed in Appendix 7. Information regarding post-study anti-cancer treatment will be collected if new treatment is initiated.

Participants who are eligible to receive retreatment with pembrolizumab according to the criteria in Appendix 7 will move from the follow-up phase to the Second Course Phase when they experience disease progression.

Survival Follow up

Participants who experience confirmed disease progression or start a new anticancer therapy, will move into the Survival Follow-Up Phase and should be contacted by telephone every 12 weeks to assess for survival status until death, withdrawal of consent, or the end of the trial, whichever occurs first. Patients will be followed for 5 years for survival.

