9.4.3 ANALYSIS OF THE SECONDARY ENDPOINT(S)

No formal hypothesis tests will be conducted for the secondary endpoints. Descriptive summarize statistics will be presented. The cumulative frequency, estimated proportion and the exact 95% confidence interval will be reported for the Disease control rate. For OS, PFS and DOR, the survival probability (Kaplan-Meier survival curve) will be calculated by the Kaplan-Meier method, the survival curve and the median survival time will be reported with the corresponding 2-sided 95% Brookmeyer-Crowley's Confidence Interval if feasible.

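### PFS and DoR are defined without death as an event, so both are biased upward whenever a patient dies without documented progression; the PFS censoring date is also undefined

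*Combined protocol and SAP*

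**What the plan says.** Section 9.1 defines three time-to-event endpoints side by side:

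- OS: "Overall Survival (OS) from the initiation of therapy to the date of death or to the date of last follow-up".
- PFS: "Progression Free Survival (PFS) from the initiation of therapy to the date of progression or to the date of last follow-up".
- DoR: "Duration of response (DoR) defined as the time from documentation of tumor response to disease progression".

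The synopsis (Section 1.1) has the same PFS and DoR definitions. So does the Section 3 table, where the PFS entry begins "Progression Free Survival (PFS) from the initiation of therapy to the" and continues in the same way. This is therefore not a slip in one place.

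Section 9.4.3 states: "For OS, PFS and DOR, the survival probability (Kaplan-Meier survival curve) will be calculated by the Kaplan-Meier method". It does not say what counts as an event or when a patient is censored, and no other section does. It also states: "No formal hypothesis tests will be conducted for the secondary endpoints".

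On assessments, Section 6.1 says "Restaging will occur every 9 weeks". Section 8.1.2.6.2 continues imaging every 12 weeks in patients who stop treatment without progression, but only until a new anticancer treatment or another listed event. Section 6.4.1 then limits follow-up to survival. Under Section 8.1.4.3, patients who progress or "start a new anticancer therapy, will move into the Survival Follow-Up Phase and should be contacted by telephone every 12 weeks", and survival follow-up lasts 5 years.

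**The concern.** Death is the event for OS and is absent from PFS and DoR in the same list. A programmer who follows the text would censor a patient who dies without a scan showing progression, and would in effect estimate time to progression under the name of PFS. DoR has the same gap and no censoring date at all.

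The plan leaves room for such deaths. The first on-study scan is at 9 weeks (Section 8.1.2.6.1), and Section 9.3 analyses everyone who received any treatment, so a death before the first scan is in the PFS set. The end-of-treatment scan is not mandatory if imaging was done in the previous 8 weeks, so a patient who stops for clinical decline may die with no documented progression.

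A second, separate question concerns PFS only. Last follow-up is not tied to a tumour assessment. If it is the same date as for OS, a patient who starts a new therapy without progression adds months with no imaging as progression-free time.

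Section 3 presents PFS, DoR and DCR as preliminary efficacy data, and Section 6.1 schedules interim looks at OS and PFS at 12 and 24 months. A PFS that is too long would feed those looks and later planning.

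**Working it through.** **1. The plan's own figure.** The only design figure is 26 patients for ORR 0.25 against 0.45, one-sided alpha 0.1, power 0.8 (Section 9.2). The exact binomial rule of at least 10 responders in 26 gives alpha 0.0909 and power 0.8064, so the figure reproduces. It does not depend on PFS or DoR. No design figure is given for either.

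**2. Direction.** Kaplan-Meier multiplies factors (1 − d/r), where d is events and r is patients at risk. Turning a death from an event into a censoring at the same date leaves every r unchanged and removes from d, so the curve can never be lower. With no such death there is no change.

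**3. Size under constant hazards.** Let m be the true median with deaths counted, and f the share of PFS events that are deaths without documented progression. The total hazard is ln 2/m. Censoring the deaths leaves hazard (1−f)·ln 2/m, hence median m/(1−f), and 6-month PFS of 2^(−6(1−f)/m) with m in months. The documents give neither f nor m. With m = 3 months assumed (true 6-month PFS 25.0%):

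| Assumed f | 1/(1−f) | Median, months | 6-month PFS |
|---|---|---|---|
| 5% | 1.053 | 3.16 | 26.8% |
| 10% | 1.111 | 3.33 | 28.7% |
| 20% | 1.25 | 3.75 | 33.0% |
| 30% | 1.429 | 4.29 | 37.9% |

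The factor does not depend on m, and it applies to DoR under the same assumption.

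**4. With 9-weekly scans.** Simulated trials of 26 patients used the same assumed 3-month median, with progression recorded at the next scan (9 weeks = 63/30.4375 = 2.07 months). Here f is the share of the underlying hazard. Deaths can also precede the scan that would have shown progression, so their share of observed events is larger than f.

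| Assumed f | 6-month PFS, deaths as events | 6-month PFS, deaths censored |
|---|---|---|
| 5% | 0.377 | 0.404 |
| 10% | 0.369 | 0.422 |
| 20% | 0.353 | 0.463 |
| 30% | 0.340 | 0.515 |

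The typical (median) trial median stayed at the second scan (4.14 months) under both rules for f up to 20%, and moved to the third (6.21 months) only at 30%. The bias shows in the curve before it shows in the median.

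**5. Last follow-up, if read as for OS.** Add an assumed 5% per month starting a new therapy without progression, with on average 6 further months of survival contact. At f = 20%, 6-month PFS is 0.342 under the standard rule, 0.462 with deaths censored, and 0.522 if the leavers are also carried to last follow-up.

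**6. Chance that the problem arises at all.** The probability of at least one death without documented progression among n patients at per-patient risk q is 1 − (1−q)^n. For PFS, n = 26. For DoR, responders number about 26 × 0.25 = 6.5 to 26 × 0.45 = 11.7, so roughly 7 to 12.

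| Assumed q | PFS, n = 26 | DoR, n = 7 to 12 |
|---|---|---|
| 5% | 73.6% | 30% to 46% |
| 10% | 93.5% | 52% to 72% |
| 20% | 99.7% | 79% to 93% |

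As a rough indication only, Section 2.2 cites median OS of 5.3 months (phase III nivolumab) and 11.4 months (phase 1b pembrolizumab). Under a constant hazard, 1 − 2^(−2.07/5.3) = 24% and 1 − 2^(−2.07/11.4) = 12% would die before day 63. These are shares of patients, not f. ECOG 0 to 1 eligibility and unscheduled scans could lower them here.

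**The case against.** The strongest reply is that little depends on these definitions. Both endpoints are secondary and untested, and Section 3 says the study is not powered to compare survival or PFS with other regimens. The primary test and the safety lead-in do not use them. Deaths are not hidden either: OS is reported, and Section 9.4.5 tabulates deaths on treatment, within 30 days and overall. All of this stands, and it lowers the severity.

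One may also say that the name of PFS implies that death counts. The written definition omits it in three places while OS names it, so the name alone is not a safe guide.

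Four stronger readings are tempting but not supported:

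- A reader might infer that both endpoints are certain to be overstated. The bias needs at least one qualifying death (or, for PFS, a patient carried past the last scan). For DoR, with few responders, there may be none.
- A reader might infer that telephone time will count as progression-free. Section 8.1.4.3 separates imaging follow-up visits from survival follow-up, and last follow-up for PFS could mean the former. The text is undefined. Only patients who start a new therapy without progression are exposed, and the documents give no frequency for them.
- A reader might settle on one inflated median. Any single value rests on chosen shares of deaths and leavers, so only a range is defensible.
- A reader might call such deaths common here, or the result not comparable with published PFS. The documents do not establish either.

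**Conclusion.** The point holds. Taken literally, the definitions make PFS and DoR times to progression, and both estimates are biased upward whenever a patient dies without documented progression. The direction is certain given such a death; the size cannot be derived from the documents. Under constant hazards, and for assumed f from 5% to 30%, the median is inflated by about 5% to 43%, although with 9-weekly scans the observed median may not move at small f. At least one such death is likely for PFS at a per-patient risk of 5% or more, and less sure for DoR.

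The undefined last-follow-up date is an ambiguity in PFS alone. It adds upward bias only if it is read as in the OS definition and some patients start a new therapy without progression.

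This is a should-fix. It changes how secondary, descriptive results can be read, not the ORR test or the 26 patients.

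**What to change.** Use identical text in Sections 1.1, 3 and 9.1, and carry it into 9.4.3:

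- **PFS:** from initiation of therapy to first RECIST 1.1 progression or death from any cause, whichever is first.
- **DoR:** from first documented response to RECIST 1.1 progression or death from any cause, whichever is first.
- **Censoring for both:** patients without an event are censored at the last adequate tumour assessment before any new anticancer therapy. State how missed scans are handled.
- **Sensitivity analysis:** censoring at new therapy is a convention and may itself be informative, so add an analysis that treats it differently, for example counting new therapy as an event.
- **OS:** keep last follow-up as the censoring date here only.

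The cost is a few sentences and one extra descriptive analysis. No new data are needed, and the sample size and ORR test do not change. The small downside is that reported PFS and DoR may be shorter. The change should be made before the outcome data are examined, so that the event rules are not chosen with the results in view.
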